7.2.2 Exclusion Criteria

Patients will be excluded from the study if they are currently enrolled in a study that includes evaluation of other restorative materials or systems involving posterior teeth. Patients will be excluded if they have a documented history of any adverse reaction to clinical materials of the type to be used in the study; is an irregular dental attendee; exhibits sensitivity in test teeth during screening visit; and the study teeth are thought to have poor access. Early caries lesions with demineralization seen on occlusal surfaces will be excluded from participation, along with white spot lesions from hypoplasia or fluorosis. Patients refusing radiograph exam will also be excluded from the study as well as pregnant female participants.

8 Clinical Evaluations

8.1 Baseline Records (*Radiography*)

Additional radiographs will not be taken for purpose of the trial only, they will be performed as part of standard of care. The policy described below reflects the widely accepted, current best practice regarding detection, diagnosis and monitoring of approximal lesions. Standardized diagnostic bitewing radiographs will be taken using an aiming device. The device facilitates optimal direction of the x-ray beam and thus leads to optimal diagnostic representation of the caries lesion.

Radiographic evaluation of the lesions and the quality of the adjacent enamel contact surface by standardized bitewing radiographs at baseline will be used to detect and diagnose the caries and monitor lesion change. An extensive review of the scientific evidence supports the importance of initial bitewings and radiographic recall examinations for description of caries progression.⁴⁹⁻⁵³ Both, the guidelines by Pitts and Kidd⁴ widely used in Europe, and the ADA/FDA-coordinated guidelines⁵⁴ advise that in high risk children (age 10-16) the interval should be 6-12 month. The proposed timing of bitewings in our study (baseline and at yearly intervals) falls well within these guidelines. They rather represent a minimum of the advised frequency for a caries-prone study population of adolescents and young adults in the age range of 6-13 years.

8.2 Clinic visits

A trained study clinician will perform all standard clinical assessments of study lesions in groups 1 and 2, including visual exam and radiograph exam. The study clinician will provide Icon treatment to all study participants randomized to study arm 1 after the radiograph and visual exam. The study clinician will provide oral hygiene instruction and topical fluoridation therapy (Duraphat fluoride varnish) to all study participants randomized to study arm 2 after the radiograph and visual exam.

A trained study clinician will capture the SFE laser optical device image of the study lesions from all study participants. The study examiner will be trained and calibrated by the HPL research team prior to start of study. SFE laser optical device image diagnoses from baseline will be compared to diagnoses from radiograph and visual exams from chart review from the same visit.

Table 8.2 Overview of the procedures during each visit

Procedure	Screening visit	Baseline and Intervention	12 Month Follow-up	24 Month Follow-up
Time		D-0	M 12 (± 3 m)	M 24 (± 3 m)
Patient information	x			
Oral examination	x		x	x
Informed consent	x			
Medical history	x			
Inclusion and exclusion criteria	x		x	x
Selection of eligible lesions	x			
Caries risk assessment	x			
Placing ortho spacers(tx group) D-21 to -7 prior to BI		x	x	x
Randomization	x			
Radiographic examination		x	x	x
Examination by SFE Before spacers placed	(x)*	x		
Examination by SFE Before & After Icon placed		x	x	x
Examination by SFE		x		
Visual Assessment of lesion		x	x	x
Intervention (Infiltration) (EXPERIMENTAL)		x		
Instruction for oral health care		x	x	x
Record of adverse effects		x	x	x
Fluoridation (CONTROL)		x	x	x

*Can be done at screening or baseline appointment

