9.1 Screening Visit

The screening phase allows confirmation of subject eligibility for the trial based in inclusion and exclusion criteria. Screening includes patient information, eligible lesions are evaluated by a study investigator and randomly selected for treatment.

Upon successful completion of the informed consent process by a parent/legal guardian, the participant will be enrolled in the study and randomized to an intervention group. Both groups 1 and 2 will return to clinic 2 weeks prior to intervention baseline visit for a pre-study visit. During this visit orthodontic spacers will be placed interproximally in the study lesion area between the primary molars. The spacer will be maintained in the interproximal area until the patient returns for the intervention baseline visit. The spacer is non-invasive and placed to separate the teeth for better access during the intervention baseline visit for improved visualization and access for Icon/fluoride application. Once the spacer is removed the space will close naturally within 3-4 weeks.

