9.4 Intervention Visit

9.4.1 Intervention Site “TREATMENT”

All groups will undergo visualization of lesions with radiograph exam, visual exam, and SFE laser optical device exam. 2 weeks prior to the SFE laser optical device exam orthodontic rubber spacers will be inserted next to the study lesions to separate the proximal space for better visualization. The initial SFE exam will occur prior to tooth separation at this visit.

Prior to Icon placement, SFE laser optical device will be performed. The study clinician will provide Icon treatment to all early lesions randomized to study arm 1 after the radiograph and visual exam and a post SFE laser optical device will be performed. The test lesions will be treated using Icon (DMG, Hamburg, Germany) following the instruction for use.

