9.4.2 Intervention Site “CONTROL”

The study clinician will provide oral hygiene instruction and topical fluoridation therapy (Duraphat fluoride varnish; Colgate Oral Pharmaceuticals, New York, NY, United States) to all study participants randomized to study arm 2 after the radiograph, visual exam and SFE Laser Exam. The initial SFE exam will occur at this visit.

Topical fluoridation treatment will be provided is varnish (Duraphat) per manufacturer's instructions.

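### The protocol contradicts itself on when the initial SFE image is taken relative to tooth separation and on which arm is separated, so SFE images may not be comparable between arms or visits

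*Combined protocol and SAP*

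**What the plan says.** Five places in the protocol govern the initial SFE image and the spacers.

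- **Table 8.2 (section 8.2), SFE row.** The row "Examination by SFE Before spacers placed" is ticked under Screening, in brackets with an asterisk, and under Baseline and Intervention, which is timed D-0. The footnote reads "Can be done at screening or baseline appointment".
- **Table 8.2, spacer row.** "Placing ortho spacers(tx group) D-21 to -7 prior to BI". The tick stands in the Baseline and Intervention column and at both follow-ups. The table has no column for a separate spacer visit.
- **Section 9.1.** "Both groups 1 and 2 will return to clinic 2 weeks prior to intervention baseline visit for a pre-study visit". Spacers go in at that visit, and "The spacer will be maintained in the interproximal area until the patient returns for the intervention baseline visit". After removal the gap takes 3 to 4 weeks to close.
- **Section 9.4.1 (treatment site, under Intervention Visit).** "2 weeks prior to the SFE laser optical device exam orthodontic rubber spacers will be inserted next to the study lesions", and then "The initial SFE exam will occur prior to tooth separation at this visit".
- **Section 9.4.2 (control site).** "The initial SFE exam will occur at this visit". Nothing is said about separation.

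Section 9.5 then places follow-up spacers only beside lesions treated with Icon. Sections 8.2 and 11.4.3 compare SFE diagnoses with the radiographic and visual diagnoses of the same visit. The SAP compares change in SFE lesion depth after 1 and 2 years with change on radiographs.

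**The concern.** The protocol gives better visualization as the reason for separating the teeth (9.1, 9.4.1, 9.5). By its own reasoning, then, an image of a closed contact and an image of a separated one are different measurements. Agreement between SFE and clinical measures is Specific Aim II, which section 6.2 lists among the primary endpoints.

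If contact state varies with the visit chosen or with the arm, an apparent difference in SFE performance or in SFE depth change could reflect the spacer and not the lesion. A before-spacer image that is missed at baseline cannot be recovered once the tooth has been separated and treated. Neither 8.2 nor 11.4.3 tells the analyst which baseline SFE image to use, and nothing in the text asks for contact state to be recorded.

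**Working it through.** No sample size, power or alpha figure enters this point, so there is no plan figure to reproduce. The check sets the passages side by side.

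**Step 1: can a before-spacer image be taken at D-0?** Spacer placement is at D-21 to D-7 (Table 8.2) and the spacer stays until the intervention baseline visit (9.1). At D-0 a lesion with a spacer has therefore been under separation for 7 to 21 days. Taking the spacer out at that visit does not restore the contact, because closure takes 3 to 4 weeks (9.1). For such a lesion the D-0 tick and the baseline option in the footnote cannot be carried out as labelled.

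**Step 2: which lesions have spacers?** Table 8.2 restricts them to the treatment group, and 9.5 to Icon-treated lesions at follow-up. Section 9.1 sends both groups to the spacer visit. These statements cannot all hold.

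**Step 3: contact state at the first SFE image.** Inputs: two spacer readings (Table 8.2; section 9.1) and three times for the Icon arm's first image (screening; spacer visit before placement; D-0). The control arm's first image is held at the intervention visit, as 9.4.2 states. This gives 2 × 3 = 6 combinations.

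| Spacers in | Icon first SFE at | Icon contact | Control contact | Arms |
|---|---|---|---|---|
| Icon arm only | Screening | closed | closed | same |
| Icon arm only | Spacer visit, before placement | closed | closed | same |
| Icon arm only | D-0 | separated | closed | differ |
| Both arms | Screening | closed | separated | differ |
| Both arms | Spacer visit, before placement | closed | separated | differ |
| Both arms | D-0 | separated | separated | same |

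The arms differ in 3 of 6. In the last row they match, but no before-spacer image exists in either arm. So 3 + 1 = 4 of 6 combinations give either a mismatch or the loss of that image. The count describes readings of the text; it is not a probability.

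**Step 4: follow-up.** Under 9.5, Icon lesions are separated at 12 and 24 months and control lesions are not. If 9.1 was followed at baseline, control lesions would go from separated at D-0 to closed at follow-up, while Icon lesions could be separated throughout. The SFE depth change in the SAP would then compare unlike images in one arm.

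**Step 5: same-visit comparator.** Table 8.2 schedules the radiographic examination and the visual lesion assessment from baseline on, not at screening. An SFE image taken at screening therefore has no same-visit comparator in that table. Section 7.1 does mention bitewings in the enrollment phase, so one may exist in practice, but the schedule does not provide it.

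**Step 6: lesions exposed.** Section 9.3 assigns 25 lesions per arm. The documents do not say how often each footnote option will be used, so the number affected runs from 0 to 25 of 25 in either arm, depending on the reading.

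**The case against.** The strongest reply is that the footnote has a harmless reading. Table 8.2 already puts a pre-D-0 procedure, spacer placement, in the Baseline and Intervention column. The baseline appointment could thus include the spacer visit, and the visit meant in 9.4.1 could be the spacer visit named in the sentence before. Both readings are possible, so the footnote alone does not prove an impossible schedule. They do not settle the matter. The column is timed D-0, 9.1 gives the two visits different names, and 9.4.1 stands under the intervention visit. Even on the harmless reading, 9.4.2 still leaves the control image at the intervention visit, where 9.1 would have those teeth separated.

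A reader might infer more than the text supports:

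- *That initial images necessarily differ by arm.* They do not if only Icon lesions get spacers and 9.4.1 is followed; then both arms are closed at the first image.
- *That every D-0 image follows 7 to 21 days of separation, or that all closed-contact images would be lost.* Neither holds for control lesions without spacers.
- *That the plan pools the two kinds of image.* Table 8.2 keeps separate SFE rows, and no passage states pooling. The gap is that the comparison does not say which image it uses.

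**Conclusion.** The point holds as an internal contradiction with a possible consequence. Table 8.2, 9.1, 9.4.1, 9.4.2 and 9.5 cannot all be followed. For any lesion with a spacer, a before-spacer image at D-0 cannot be obtained. Depending on the reading adopted, initial images may be closed in one arm and separated in the other, or the before-spacer image may be missing; follow-up images may also differ by arm.

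This rests on two assumptions: that the control arm's first image is taken at the intervention visit, as 9.4.2 states, and that contact state affects the image, as the protocol's reason for separating implies. The size of any effect on SFE diagnoses cannot be derived from the documents.

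Specific Aim II and the SFE depth-change comparison are affected. The radiographic primary outcome does not depend on this point. It should be corrected, but it does not threaten the main treatment comparison.

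**What to change.** 1. Reconcile Table 8.2, 9.1, 9.4.1, 9.4.2 and 9.5 on which arm has spacers and when. The choice belongs to the sponsor and the investigator; this review does not propose one.
2. Add a pre-study visit column to Table 8.2. Reword the footnote, the D-0 tick and 9.4.1 so that the before-spacer SFE image falls at an appointment before the spacer is placed.
3. State in 9.4.2 the contact state of the control lesions' initial image, consistent with the reconciled spacer rule.
4. Add a CRF field for contact state (closed or separated) for each SFE image, at baseline and follow-up.
5. In 8.2 and 11.4.3, name the SFE image that is compared with the baseline radiograph and visual examination, allowing for the missing comparator at screening in Table 8.2. Report closed-contact and separated images separately.

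The cost is wording, one table column and one CRF field. Separate reporting leaves fewer images in each comparison, so each estimate of agreement will be less precise.

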8.3 Evaluation Categories

8.3.1 History Taking (Interview)

- Oral Health care behavior

8.3.2 Diet

- Snacking: frequency and content
- Softdrinks: frequency and sipping

8.3.3 Local Ecology

- No other scores will be documented

8.3.4 Caries Experience

- Ekstrand's criteria
- Additionally, the caries experience and caries risk shall be recorded for each patient in the caries activity form supplied by DMG.

8.3.5 Individually standardized record (Radiographs)

- DMG criteria for Icon treatment

8.4 Evaluation Criteria

8.4.1 Preamble

None

8.4.2 Eligibility Criteria

To be eligible for the study, each participant must meet preliminary eligibility criteria and the participant and the guardian must be willing to sign a statement of informed consent. This will document the agreement of the participant to participate in the studies activities.

[figure not shown]
Additionally, participants will be asked by study personnel not to participate in any other therapeutic research studies during the participant's follow-up period from baseline to the 24 month visit.

Table 8.4.2.1 Ekstrand's criteria for visual examination and evaluation of carious lesions

0	No or slight change in enamel translucency after air drying (5 s)
1	Opacity (white) hardly visible on the wet surface, but distinctly visible after air drying
2	Opacity (white) distinctly visible without air drying
2a	Opacity (brown) distinctly visible without air drying
3	Localized enamel breakdown in opaque or discoloured enamel and/or greyish discolouration from the underlying dentine
4	Cavitation in opaque or discoloured enamel exposing the dentine beneath

Table 8.4.2.2 Criteria used in the radiograph examination

E1	Radiolucency confined to the outer half of enamel
E2	Radiolucency involving the inner half of enamel
D1	Radiolucency in the outer third of dentin
D2	Radiolucency in the middle third of dentin
D3	Radiolucency in the inner third of dentin

**Figure 3: DMG criteria for treatment planning for Icon infiltration therapy. Adopted from (7).**

NOTE: For study purposes only we will use criteria in E1 and E2 only.

8.4.3 Local ecology

- none

9 Clinical Measurements and Procedures

9.1 Screening Visit

The screening phase allows confirmation of subject eligibility for the trial based in inclusion and exclusion criteria. Screening includes patient information, eligible lesions are evaluated by a study investigator and randomly selected for treatment.

Upon successful completion of the informed consent process by a parent/legal guardian, the participant will be enrolled in the study and randomized to an intervention group. Both groups 1 and 2 will return to clinic 2 weeks prior to intervention baseline visit for a pre-study visit. During this visit orthodontic spacers will be placed interproximally in the study lesion area between the primary molars. The spacer will be maintained in the interproximal area until the patient returns for the intervention baseline visit. The spacer is non-invasive and placed to separate the teeth for better access during the intervention baseline visit for improved visualization and access for Icon/fluoride application. Once the spacer is removed the space will close naturally within 3-4 weeks.

9.2 Selection of Lesions (Screening visit only)

Study participants will be recruited from the Resident Clinic at the Center for Pediatric Dentistry at new patient or non-invasive recall visits. Resident clinicians and the research team will assist recruitment by identifying potential candidates with appropriate interproximal early caries lesions. All participants will be in general good health, aged 6-13 years, and enrolled into the study upon successful completion of the informed consent process.

9.3 Randomization

25 non-cavitated early caries lesions will be randomly assigned, using a random numbers table, to study arm 1) the Icon treatment group; and 25 non-cavitated early caries lesions will be randomly assigned, using a random numbers table, to study arm 2) the Control group (OHI and topical fluoridation).

9.4 Intervention Visit

9.4.1 Intervention Site “TREATMENT”

All groups will undergo visualization of lesions with radiograph exam, visual exam, and SFE laser optical device exam. 2 weeks prior to the SFE laser optical device exam orthodontic rubber spacers will be inserted next to the study lesions to separate the proximal space for better visualization. The initial SFE exam will occur prior to tooth separation at this visit.

Prior to Icon placement, SFE laser optical device will be performed. The study clinician will provide Icon treatment to all early lesions randomized to study arm 1 after the radiograph and visual exam and a post SFE laser optical device will be performed. The test lesions will be treated using Icon (DMG, Hamburg, Germany) following the instruction for use.

9.4.2 Intervention Site “CONTROL”

The study clinician will provide oral hygiene instruction and topical fluoridation therapy (Duraphat fluoride varnish; Colgate Oral Pharmaceuticals, New York, NY, United States) to all study participants randomized to study arm 2 after the radiograph, visual exam and SFE Laser Exam. The initial SFE exam will occur at this visit.

Topical fluoridation treatment will be provided is varnish (Duraphat) per manufacturer's instructions.

9.5 Follow-up Evaluations

Follow-up assessments will occur at months 12 and 24 from baseline +/- 3 months. Study patients will be reminded of their follow up visit. The following will occur at all follow-up visits:

- Two weeks prior to the appointment (-21 to -7 days) Orthodontic rubber spacers will be inserted next to the iconized lesions to separate the proximal space for better visualization.
- Radiograph exam of study lesion
- Visual exam of study lesion
- SFE laser optical device imaging of study lesion

Results are documented in CRF (Appendix A1).

If study lesions are noted to be progressing at any point the study clinician will refer the participant for standard-of-care treatment to the CPD Resident Clinic. Progression is defined as lesion changes

from E2 to D category according to DMG's criteria. The study participant will no longer participate in the study at this point.

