The primary endpoint in this study is the proportion of study lesions that have progressed, whereby a difference in caries progression of 40% after 2 years between resin infiltrated teeth and control will be assumed. This difference is based on a previous infiltration study by Ekstrand et al. [45] who reported a 1-year difference in caries progression in primary teeth of 39% (resin infiltration (23%) vs. control (62%)), which was furthermore comparable to results obtained in young adults. Martignon et al [42] for example reported a difference in caries progression in permanent teeth of 37% and 38% after 1 and 2 years respectively; and Meyer-Lueckel et al. of 30% after 18 months.

Based on an assumed difference in caries progression of 40% between resin infiltrated teeth and control, with alfa = 0.05 and a power of 80% the calculated sample size (t-test; matched pairs) would be 42 lesions to find significant differences. To allow for a potentially attrition rate of at least 20% over a period of 2 years a total of 50 lesions will be included.

Statistical Analysis

All evaluations are performed by one trained examiner. The primary outcome is proportion of study lesions that progressed after 2 years as measured via dental examination and pairwise comparison of radiographs. Differences between groups will be tested using Fisher's exact test.

Secondary outcomes are the proportion of study lesions that progressed after 1 year as well as change in categorical lesion depth (progression to next depth category lesion; E1->E2->D1->D2->filling) after 1 and 2 years as measured by pairwise comparison of radiographs. In addition, the change in categorical lesion depth will be determined via SFE laser optical device imaging after 1 and 2 years and compared to the change in categorical lesion depth as measured by pairwise comparison of radiographs. Differences in categorical lesion depth will be analyzed with Chi-square tests with 95% confidence interval (95% CI) and P = .05.

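### Spacers at months 12 and 24 are scheduled for Icon lesions only, so visual and SFE follow-up assessments are made under different conditions in the two arms, and the SFE rows of Table 8.2 contradict the text

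*Combined protocol and SAP*

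**What the plan says.** **Spacers at follow-up.** Section 9.5 describes the months 12 and 24 visits: "Orthodontic rubber spacers will be inserted next to the iconized lesions to separate the proximal space for better visualization". The spacer row of Table 8.2 (section 8.2) is labelled "Placing ortho spacers(tx group) D-21 to -7 prior to BI" and is ticked at baseline, month 12 and month 24. No section schedules follow-up spacers for control lesions.

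**Spacers before baseline.** Section 9.1 covers both arms: "Both groups 1 and 2 will return to clinic 2 weeks prior to intervention baseline visit for a pre-study visit". Spacers are placed at that visit, and their purpose is given as "placed to separate the teeth for better access during the intervention baseline visit for improved visualization and access for Icon/fluoride application". Section 9.4.1 likewise refers to all groups and to the study lesions generally. The treatment-group label in Table 8.2 conflicts with this at baseline too.

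**SFE at follow-up.** Table 8.2 has three SFE rows. The only one ticked at months 12 and 24 is "Examination by SFE Before & After Icon placed". The general SFE row is ticked at baseline only, and "Examination by SFE Before spacers placed" only at screening or baseline. Section 9.5, by contrast, lists "SFE laser optical device imaging of study lesion" for every follow-up visit without naming an arm. Section 8.2 has SFE images captured from every participant. Section 11.4.3 compares SFE with the other examinations at each time point, and the SAP analyses SFE change after 1 and 2 years.

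**Outcomes.** Aim I (6.2.1) is caries arrest on bitewings. The SAP defines the primary outcome as lesions progressed after 2 years "as measured via dental examination and pairwise comparison of radiographs". Section 11.4.1 tests the secondary outcomes by treatment group.

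**The concern.** By the protocol's own account, separating the teeth improves the view of the proximal surface, so it is a condition of measurement. If that condition depends on the arm, a difference in what is recorded can arise with no difference in the lesions.

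The outcomes most exposed are those in section 6.3 that require seeing the surface: white spot reversal, colour match and staining, surface quality, and SFE visualization and depth. Change within the control arm is also affected, because control lesions are separated at baseline and not afterwards. In addition, a spacer present in one arm only, or the gap it leaves, tells the SAP's single examiner which lesions were infiltrated.

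The SFE rows raise a second problem. A site working from Table 8.2 alone could omit follow-up SFE in control lesions, and images missed at a visit cannot be recovered.

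**Working it through.** The plan gives no figure for this point, so the check sets the sections side by side.

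| Item | Icon lesions | Control lesions |
|---|---|---|
| Spacers before baseline, 9.1 and 9.4.1 | yes | yes |
| Spacers before baseline, Table 8.2 | yes | no (treatment-group row) |
| Spacers at months 12 and 24, 9.5 | yes | not scheduled |
| Spacers at months 12 and 24, Table 8.2 | yes | not scheduled |
| SFE at months 12 and 24, 9.5, 8.2 text, 11.4.3, SAP | yes | yes (no arm restriction; the 8.2 text names no visit) |
| SFE at months 12 and 24, Table 8.2 | yes (Icon-placement row) | not ticked |
| Bitewings and visual assessment at months 12 and 24, Table 8.2 | yes | yes |

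**Step 1: spacers.** At follow-up, text and table agree that only Icon lesions are separated, so a slip in one place does not explain it. At baseline, text and table disagree.

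**Step 2: effect on a visually assessed outcome.** Let p be the true proportion with a finding, Se the sensitivity and Sp the specificity of the examination. The recorded proportion in an arm is

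p·Se + (1 − p)·(1 − Sp).

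If p is the same in both arms, the recorded difference, Icon minus control, is

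p·(Se_Icon − Se_control) − (1 − p)·(Sp_Icon − Sp_control).

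This is zero when both arms are examined in the same way. If separation improves both sensitivity and specificity, the first term raises the Icon proportion and the second lowers it. The documents give neither quantity, with or without separation, so neither the size nor the sign can be computed.

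**Step 3: reach into the primary outcome.** Bitewings are scheduled without restriction by arm. Aim I is radiographic, section 9.5 defines progression by radiographic category, and section 11.3 assesses bitewings. The asymmetry enters the primary outcome only through the dental examination in the SAP definition, and the SAP does not say how examination and radiograph are combined.

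**Step 4: change within the control arm.** Under 9.1 the baseline visual assessment follows separation, and the follow-up assessments do not. For SFE, the plan also has an image taken before separation, which would match the control follow-up conditions. It does not say which baseline image is the reference.

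**Step 5: SFE rows.** No infiltration is scheduled at months 12 and 24, so a row about imaging before and after Icon placement cannot apply literally there. The general SFE row may have been meant. If the table were followed as printed, 25 of the 50 planned lesions would have no follow-up SFE images. The SFE-versus-radiograph comparison would then rest on at most 50 − 25 = 25 Icon lesions, before attrition.

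**The case against.** The strongest reply is that the main result is radiographic and that bitewings are taken equally in both arms. That largely stands. A reader might infer that unseparated control lesions hide progression, shrink the treatment difference and so cost the primary test its power. The documents do not support this. The progression rates in section 4.3.4 from which one would start (for example 24% and 62% after two years) are radiographic. A missed visual sign does not remove a radiographic progression, and nothing in the plan lets the visual examination override the bitewing. Any visual sensitivity used for such a calculation would have no source in the documents. A power figure for the primary outcome is therefore not justified.

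A second reply is that the SFE conflict is only a mislabelled row. That is probably right. The text and the SAP point to follow-up SFE in both arms, and ticks in adjacent rows should be checked against the laid-out table. A reader might also infer that the SFE comparison would be lost altogether. It would not be. The SAP compares SFE with radiographs, and Icon lesions would still supply pairs. What would go is the control lesions' contribution and any between-arm SFE comparison.

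A third reply is that masking is weak in any case. Section 8.2 has a study clinician both assess lesions and deliver the treatments. Table 8.2 schedules fluoridation for controls at follow-up, and section 11.4.2 covers only subject codes. This is correct: the spacer is an additional cue and not the origin of the gap.

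None of these replies removes the different viewing conditions for the visual and SFE outcomes.

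**Conclusion.** The point holds for the visual and SFE secondary outcomes. As written, these are assessed at months 12 and 24 on separated Icon lesions and unseparated control lesions, then compared by arm. Visual change within the control arm is affected if 9.1 governs baseline. SFE change is affected too if the separated baseline image is the reference.

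All 25 planned control lesions are involved at both follow-up visits. The size and direction of any bias are unknown. The effect on the primary outcome is limited to whatever the dental examination contributes beyond the bitewings, and no loss of power is shown.

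The SFE part is a contradiction between Table 8.2 and the rest of the plan. It is not an established omission of control imaging.

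The conclusion assumes that separation changes what is seen, which the protocol itself states as its purpose. That the spacer reveals allocation to the examiner is an inference. The correction should be made before follow-up begins, but the point does not undermine a bitewing-based primary analysis.

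**What to change.** 1. Reconcile sections 9.1, 9.4.1, 9.5 and Table 8.2 so that the separation and SFE procedure is identical in both arms at each visit. Which procedure is used is for the sponsor to decide.
2. Relabel the SFE rows of Table 8.2 so that follow-up imaging matches section 9.5 and is not tied to Icon placement. State which baseline SFE image is the reference for change.
3. Align the SAP primary outcome with Aim I by determining progression from the bitewings.
4. If the asymmetry remains, state in the SAP that between-arm differences in visual or SFE outcomes will not be interpreted.

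The cost is a correction to one table, a few paragraphs and the SAP outcome definition. Depending on the sponsor's choice, spacer steps at the two follow-up visits are either added for control lesions or dropped for Icon lesions, with SFE steps adjusted to match. No change to sample size or randomization is needed.
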